**Table 17.2.1**

		Number of Patients																	
		1	2	3	4	5	6	7	8	9	10	11	12	13	14	15	16	17	18
Number of Patients with DLTs	0	E	E	E	E	E	E	E	E	E	E	E	E	E	E	E	E	E	
	1	D	D	S	S	S	S	S	E	E	E	E	E	E	E	E	E	E	
	2	D	DU	D	S	S	S	S	S	S	S	S	S	S	S	S	E	E	
	3	DU	DU	DU	DU	D	S	S	S	S	S	S	S	S	S	S	S	S	
	4	DU	DU	DU	DU	DU	DU	D	S	S	S	S	S	S	S	S	S	S	
	5	DU	DU	DU	DU	DU	DU	DU	DU	DU	S	S	S	S	S	S	S	S	
	6	DU	DU	DU	DU	DU	DU	DU	DU	DU	DU	DU	DU	DU	DU	S	S	S	
	7	DU	DU	DU	DU	DU	DU	DU	DU	DU	DU	DU	DU	DU	DU	DU	DU	DU	
	8	DU	DU	DU	DU	DU	DU	DU	DU	DU	DU	DU	DU	DU	DU	DU	DU	DU	
	9	DU	DU	DU	DU	DU	DU	DU	DU	DU	DU	DU	DU	DU	DU	DU	DU	DU	
	10	DU	DU	DU	DU	DU	DU	DU	DU	DU	DU	DU	DU	DU	DU	DU	DU	DU	
	11	DU	DU	DU	DU	DU	DU	DU	DU	DU	DU	DU	DU	DU	DU	DU	DU	DU	
	12	DU	DU	DU	DU	DU	DU	DU	DU	DU	DU	DU	DU	DU	DU	DU	DU	DU	
	13	DU	DU	DU	DU	DU	DU	DU	DU	DU	DU	DU	DU	DU	DU	DU	DU	DU	
	14	DU	DU	DU	DU	DU	DU	DU	DU	DU	DU	DU	DU	DU	DU	DU	DU	DU	
	15	DU	DU	DU	DU	DU	DU	DU	DU	DU	DU	DU	DU	DU	DU	DU	DU	DU	

16												DU	DU	DU
17												DU	DU	
18														DU

**E:** Escalate to the next higher dose; **S:** Stay at the same dose; **D:** De-escalate to the previous lower dose; **DU:** De-escalate to the previous lower dose and the current dose will never be used again in the trial;

No new cohort of patients will be treated until the previous cohort has been fully evaluated for toxicity. All patients treated to determine the MTD will be part of the escalation portion of the trial.

Once the MTD is reached, the safety data will be analyzed and the expansion component of the study will be completed to assess tolerability and efficacy. Patients in the expansion component of the study will initiate study treatment at the respective MTD. Note that dose reduction within individual patients is allowed in the expansion component of the study. Dose reduction will be required for a given patient in case of grade 3 or 4 toxicities, or if grade 2 creatinine, bilirubin, AST, ALT, hyperphosphatemia or grade 2 GI toxicity lasting more than 2 weeks.

Since a phase II study is currently being planned, tolerability and experience with these combinations over at least 8-16 weeks is desirable. A period of 8 weeks was deemed acceptable for assessment of study drug tolerability. Hence, we are proposing a modified definition of an MTD, to ensure tolerability of study drugs for a more prolonged period of time in anticipation of future phase II trials. We plan to treat at least 20 patients as part of the expansion portion of the study. For tolerability assessment, patients in the escalation portion of the trial that are treated at the MTD will be included in the tolerability analysis.

#### Justification for RP2D based on $\geq 15$ out of 20 Tolerant Patients

	0.3	True probability of tolerability at MTD						
		0.5	0.7	0.75	0.8	0.9	0.99	
Probability of observing $\geq 15/20$ tolerable patients	0.00004	0.02	0.42	0.62	0.80	0.99	1.00	

#### Two-sided 95% Wilson Confidence Intervals\* for the Probability of Treatment Tolerance based on $\geq 15$ Tolerant Patients out of 20

Observed # of tolerant patients	95% Wilson confidence interval	
	Lower bound	Upper bound
15	0.53	0.89
16	0.58	0.92
17	0.64	0.95
18	0.70	0.97
19	0.76	0.99
20	0.84	1.00

\* We chose to calculate and report the Wilson score confidence intervals because of their good coverage properties, especially when the true proportions are at extreme values such as

being equal to or close to 1

([http://en.wikipedia.org/wiki/Binomial\\_proportion\\_confidence\\_interval](http://en.wikipedia.org/wiki/Binomial_proportion_confidence_interval)).

The recommended dose for phase II trials will be defined as the highest dose (at or below the MTD) at which  $\geq 15$  patients treated at the MTD (including patients from the escalation portion treated at that same dose level) can tolerate treatment for a minimum of 8 weeks in a row without development of the previously cited toxicities. The dose that will be used in the phase II study will be the most tolerable (i.e. with the least amount of  $\geq$  Grade 2 toxicities), as tested in this study. Study drugs will be given at the specified doses above until disease progression or unacceptable toxicity. As long as the above parameters are fulfilled (i.e. at least 15 out 20 patients are able to safely tolerate the combination at a given dose level stipulated by the study for 8 weeks in a row) the dose of study drugs in the expansion portion of the study (i.e. the highest tolerable dose; not necessarily the MTD) will move forward in phase II studies.

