## 7.5 Definition of Maximum Tolerated Dose (MTD)

The MTD will be defined as the highest dose at which 20% of the patients experienced a DLT. The first cohort of patients (3 patients) will be started at dose level 1, and each patient will be observed for 4 weeks on the specified dose. No new cohort of patients will be treated until the previous cohort has been fully evaluated for toxicity and a dose escalation decision has been made. Routine updates regarding patient and study status will be conducted.

Once the MTD is reached, the safety data will be analyzed and the expansion component of the study will be completed to assess tolerability and efficacy. Patients in the phase II portion of the study will initiate study treatment at the MTD defined in the escalation component of the trial. Note that dose reduction within patients (individually) is allowed after the 4 week DLT observation period in the escalation and in the expansion components of the study (see Dose Modification guidelines, Section 8). Intrapatient dose escalation will not be allowed. Dose reduction will be required for a given patient in case of:

- Grade 3 or 4 toxicities
- Grade  $\geq 2$  hyperphosphatemia lasting more than 21 days despite medical treatment, or
- Grade  $\geq 2$  ocular toxicity lasting more than 28 days despite medical treatment, or
- Grade  $\geq 2$  elevation of creatinine, bilirubin, AST, or ALT lasting more than 14 days despite medical treatment, or
- Grade  $\geq 2$  skin or nail toxicity for more than 28 days in a row despite optimal medical treatment, or

- Grade  $\geq$  2 GI toxicity lasting more than 14 days despite medical treatment.

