## 17.2 Sample Size and Statistical Analysis

### 17.2.1 Primary endpoint

Demographic and baseline patient characteristics will be summarized. Adverse events will be classified by type, incidence, severity, and causality. All adverse events will be summarized by patient, dose level, and disease. All patients who received at least 4 weeks of study treatment drugs (unless DLTs observed) will be included in the **safety** portion of the trial, and all patients who received at least 8 weeks of erdafitinib will be included in the **tolerability** portion of the trial.

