In the phase Ib escalation component of the trial, the MTD will be defined using the recently developed adaptive design known as the modified toxicity probability interval (mTPI) method. The mTPI design uses a Bayesian framework with a beta/binomial hierarchical model to compute the posterior probabilities of three intervals that reflect the relative distance between the toxicity rate of each dose level to the target toxicity probability. That is, the mTPI design replaces the 3 + 3 rules with a model-based inference on the toxicity probability intervals and has been shown to be safer and more reliable than the 3+3 design. The first cohort of patients (3 patients) in each arm will be started at dose level 1, and each patient will be observed for 4 weeks on the specified dose. The maximum tolerated dose (MTD) will be defined as the highest dose at which 20% of the patients experienced a DLT. The levels of uncertainty around the true target toxicity  $p_T$  are (0.05, 0.05), which define the proper dosing interval as  $(p_T - 0.05, p_T + 0.05)$ . Each cohort has 3 patients. In **Table 17.2.1**, the columns are the numbers of patients treated so far at the current dose level, and the rows are the corresponding numbers of patients experiencing toxicity. The entries of the table are dose-finding decisions—E, S, and D—representing escalating the dose, staying at the same dose, and de-escalating the dose, respectively. In addition, decision U means that the current dose level is unacceptable because of high toxicity and should be excluded from the trial. For example, when one of three patients experiences toxicity, the decision is to stay at the current dose level. This means that the next cohort of 3 patients will be treated at the same dose level currently being used. If zero of three patients experiences toxicity, the decision is to escalate. This means that the next cohort of 3 patients will be treated at the next-higher dose level. If three of three patients experiences toxicity, the decision is DU—to de-escalate to the next-lower dose level and exclude the current dose from the trial which is considered unacceptably toxic.

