### 17.3 Reporting and Exclusions

All patients included in the study must be assessed for safety, tolerability, and response to treatment, even if there are major protocol treatment deviations or if they are ineligible. Each patient will be assigned one of the following categories: 1) complete response, 2) partial response, 3) stable disease, 4) progressive disease, 5) early death from malignant disease, 6) early death from toxicity, 7) early death because of other cause, or 9) unknown (not assessable, insufficient data). All of the patients who met the eligibility criteria (with the possible exception of those who received no study medication) should be included in the main analysis of the response rate. Patients in response categories 4-9 should be considered to have a treatment failure (disease progression). Thus, an incorrect treatment schedule or drug administration does not result in exclusion from the analysis of the response and clinical benefit rate.

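### The RP2D rule is stated both as a bare count of 15 and as 15 of 20, and the 20 patients are never identified although more than 20 are planned at the MTD

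*Combined protocol and SAP*

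**What the plan says.** The decision rule is in Section 17.2.1, under the justification for the RP2D.

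- **The rule as a count.** The RP2D is the highest dose, at or below the MTD, at which 15 or more "patients treated at the MTD (including patients from the escalation portion treated at that same dose level) can tolerate treatment" for at least 8 consecutive weeks without the toxicities cited before. This is a count without a denominator.
- **The rule as 15 of 20.** A few lines later the condition is that "at least 15 out 20 patients are able to safely tolerate the combination". The heading, the table of pass probabilities and the table of Wilson intervals also use 20.
- **Who is at the MTD.** "We plan to treat at least 20 patients as part of the expansion portion of the study", and these patients start at the MTD. In addition, "patients in the escalation portion of the trial that are treated at the MTD will be included in the tolerability analysis". Section 17.2.1 also states "Each cohort has 3 patients", and the dose table in Section 7.3 shows 3 to 6 patients per level.
- **Who is in the tolerability set.** The opening of Section 17.2.1 says "all patients who received at least 8 weeks of erdafitinib will be included in the" tolerability portion. Section 17.3 says "All patients included in the study must be assessed for safety, tolerability, and response to treatment".
- **Which toxicities count.** Sections 7.5 and 17.2.1 each list toxicities that require dose reduction. Section 7.5 has "hyperphosphatemia lasting more than 21 days despite medical treatment", where 17.2.1 has more than 2 weeks. Prolonged Grade 2 ocular, skin and nail toxicity appears only in 7.5. The durations for creatinine, bilirubin, AST/ALT and GI toxicity agree.

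**The concern.** The pooled group at the MTD exceeds 20 by plan, so the two wordings are different rules. A threshold fixed at 15 gets easier to meet with every patient above 20. The lowest passing observed rate falls from 75% (15/20) to 65% (15/23) or 58% (15/26). The printed pass probabilities and intervals describe only the 15-of-20 reading.

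This rule decides whether the expansion dose goes forward to the planned phase II trial. If 15 of 24 patients tolerate treatment, the first sentence passes the dose. The second passes or fails it depending on which 20 are taken, and that choice could be made after the data are known. The 20% DLT target and the sentence preferring the dose with the fewest Grade 2 or higher toxicities are further filters, but neither fixes the denominator.

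**Working it through.** **Inputs.** Threshold 15 and the tabulated true tolerability rates are from Section 17.2.1. The number at the MTD is derived, not stated: 20 expansion patients (17.2.1) plus 3 to 6 at that level (7.3) gives 23 to 26.

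**Formula.** P(pass) = Σ C(n,k) p^k (1−p)^(n−k), summed over k = 15 to n.

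**The plan's own figure.** At n = 20, p = 0.5: (15504 + 4845 + 1140 + 190 + 20 + 1) / 2^20 = 21700 / 1048576 = 0.0207, printed as 0.02. The other printed entries also reproduce, as do the Wilson intervals (15/20: 0.531 to 0.888).

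**Count wording, 15 tolerant among all n:**

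| True tolerability | n = 20 (printed) | n = 23 | n = 24 | n = 25 | n = 26 |
|---|---|---|---|---|---|
| 0.5 | 0.021 (0.02) | 0.105 | 0.154 | 0.212 | 0.279 |
| 0.7 | 0.416 (0.42) | 0.771 | 0.847 | 0.902 | 0.940 |
| 0.75 | 0.617 (0.62) | 0.904 | 0.945 | 0.970 | 0.985 |
| 0.8 | 0.804 (0.80) | 0.973 | 0.987 | 0.994 | 0.998 |

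**Wilson 95% interval at exactly 15 tolerant.** 15/23: 0.449 to 0.812. 15/26: 0.389 to 0.745. The printed lower bound for 15 of 20 is 0.53.

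**How often the wordings disagree.** Take the 15-of-20 wording as 15 among the first 20. Passing in the first 20 implies passing in all n, so the chance of opposite verdicts is exactly the difference of the two pass probabilities.

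| True tolerability | n = 23 | n = 26 |
|---|---|---|
| 0.5 | 0.105 − 0.021 = 0.084 | 0.279 − 0.021 = 0.258 |
| 0.7 | 0.771 − 0.416 = 0.354 (unrounded inputs) | 0.940 − 0.416 = 0.523 (unrounded inputs) |
| 0.8 | 0.973 − 0.804 = 0.168 (unrounded inputs) | 0.998 − 0.804 = 0.193 (unrounded inputs) |
| 0.9 | about 0.01 | about 0.01 |

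**Sensitivity to n at p = 0.5.** n = 21: 0.039. n = 22: 0.067. n = 29: 0.500. So losing 1 or 2 of 23 to non-toxicity causes gives 6.7% or 3.9%, and losing 3 of 23 or 6 of 26 brings back 2%. The documents give no attrition figure.

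**The 8-week condition.** Suppose 26 are treated, 6 stop early for toxicity and 15 tolerate treatment. With early stoppers left out, as the opening of 17.2.1 literally reads, the result is 15/20 = 75%. With all treated patients counted it is 15/26 = 58%. This affects a 15-of-20 or proportion rule. Under a bare count, leaving out early stoppers cannot change the verdict.

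**The case against.** The strongest reply is that 15 of 20 was plainly meant. The heading, both tables and the closing sentence use 20, and the closing sentence reads as a gloss on the count. On that reading the printed 2% stands. That is probably the intent, but it does not settle the rule: the formal definition is the count, escalation patients are added explicitly, and the 20 are not named.

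Second, 23 to 26 is an inference. The 3 to 6 per level fits the 3+3 label still in Section 7.1, whereas the mTPI grid in 17.2.1 runs to 18 patients at one dose and the expansion is a minimum of 20. This stands as a caveat. The number could be higher, which loosens the count further, or lower through non-evaluable patients.

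Third, Section 7.11 already allows replacement of patients who leave for unrelated reasons in cycle 1 or receive under 75% of the intended dose. That is correct, but it covers only the first 4 of the 8 weeks, and replacement tends to keep n up.

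Fourth, the disagreement between wordings is largest near 0.7 and almost vanishes at 0.9. That is also correct, and the table shows it. The rule matters most in the range where the dose is doubtful.

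Finally, the toxicity-list mismatch is a separate matter and does not support the numbers. That is accepted. The list in 17.2.1 may be the natural referent, but the text does not say so.

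**Conclusion.** The concern holds. The RP2D rule has two wordings that give different decisions once more than 20 patients are treated at the MTD, which the plan intends. The printed operating characteristics belong to only one of them. Under the count wording, with 23 to 26 patients, the chance of passing a dose with 50% true tolerability is 10.5% to 27.9% instead of 2%. At 70% it is 77% to 94% instead of 42%. At 70% the two readings give opposite verdicts 35% to 52% of the time.

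These figures assume the count wording, the derived 23 to 26, no non-toxicity loss before week 8, and independent patients with a common tolerability rate. They ignore that the MTD was itself chosen for few DLTs among its escalation patients. Under a strict 15-of-20 reading the printed tables are right, but the plan must then say which 20. Because the rule governs the step to phase II, it should be corrected before it is applied.

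**What to change.** Choose one rule and state it once.

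**(a) Proportion.** At least 75% of all patients treated at that dose: 15/20, 16/21, 17/22, 18/23, 18/24, 19/25, 20/26. Reprint both tables for n = 20 to 26. Pass probabilities:

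| True tolerability | 18/23 | 18/24 | 19/25 | 20/26 | Printed (15/20) |
|---|---|---|---|---|---|
| 0.5 | 0.005 | 0.011 | 0.007 | 0.005 | 0.02 |
| 0.7 | 0.27 | 0.39 | 0.34 | 0.30 | 0.42 |
| 0.75 | 0.47 | 0.61 | 0.56 | 0.52 | 0.62 |
| 0.8 | 0.69 | 0.81 | 0.78 | 0.75 | 0.80 |

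The cost is a lower chance of passing a dose with good tolerability at some n, most clearly at 23.

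**(b) Fixed set.** Prespecify that the first 20 patients treated at that dose form the decision set. The printed tables then stand. The cost is that the last 3 to 6 patients at the dose do not enter the decision.

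Under either option:

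- State that patients who stop before 8 weeks for toxicity count as non-tolerant.
- State how non-toxicity stoppers are handled, including in weeks 5 to 8, which Section 7.11 does not cover.
- Align the opening of 17.2.1 and Section 17.3 with that set.
- Reconcile the lists in 7.5 and 17.2.1 so that the toxicities in the rule point to one list. Which list applies is for the sponsor to decide.

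Overall this costs wording and, for (a), two reprinted tables. No extra patients or visits are needed.

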chemotherapy, but naïve to CDK4/6 inhibitors. Patients received fulvestrant with placebo or with palbociclib. The PFS at time of interim analysis was 9.2 months in the investigational arm vs. 3.8 months for fulvestrant plus placebo arm (HR=0.42; p<0.000001). The most common grade 3 or 4 adverse events in the palbociclib-fulvestrant group were neutropenia (62.0%, vs. 0.6% in the placebo-fulvestrant group), leukopenia (25.2% vs. 0.6%), anemia (2.6% vs. 1.7%), thrombocytopenia (2.3% vs. 0%), and fatigue (2.0% vs. 1.2%). Thirty-three percent of patients had received one line of prior chemotherapy for metastatic disease. Based on these results, in February 2016 palbociclib was FDA-approved in combination with fulvestrant for second line treatment of patients with ER+/HER2-negative MBC.

Of note, the potential for a clinically significant drug-drug interaction between the CDK4/6 inhibitor palbociclib and fulvestrant is very low. A phase III trial has completed accrual, with an initial safety assessment with trough plasma concentrations demonstrating no pharmacokinetic interactions between fulvestrant and palbociclib. *In vitro* data indicate that CYP3A and SULT enzyme SULT2A1 are mainly involved in the metabolism of palbociclib. The strong CYP3A inhibitor itraconazole increased palbociclib AUCinf by approximately 87%, relative to palbociclib given alone. As expected, coadministration of rifampin, a strong CYP3A inducer, decreased palbociclib AUCinf by 85% relative to palbociclib given alone. Palbociclib is a weak time-dependent inhibitor of CYP3A following administration of the clinical 125 mg dose: palbociclib increased the midazolam AUCinf values by 61%, as compared with midazolam alone. *In vitro*, palbociclib is not an inhibitor of CYP1A2, 2A6, 2B6, 2C8, 2C9, 2C19, and 2D6, and is not an inducer of CYP1A2, 2B6, 2C8, and 3A4 at clinically relevant concentrations. *In vitro* evaluations indicated that palbociclib has a low potential to inhibit the activities of drug transporters at clinically relevant concentrations.

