Erdafitinib exhibited a dose-related increase in Cmax and area under the analyte concentration-time curve (AUC) and time-independent PK within the dose range of 0.5 to 12 mg, both after single and multiple daily dosing. The actual sampling time to reach maximum concentration (tmax) ranged between 2-4 hours (erdafitinib as tablet), independent of the studied formulations. PK was characterized by moderate intersubject variability (CV% 31-39%) and low intra-subject variability (9-10%). Erdafitinib is primarily excreted in feces either as unchanged drug or as metabolites. In vitro data indicated that CYP3A and 2C9 are involved in erdafitinib metabolism. 70% and 20% of the radioactivity was recovered in feces and urine, respectively, with approximately 11% of unchanged drug recovered in urine. Erdafitinib is highly bound to plasma proteins, especially to  $\alpha$ 1-AGP (fraction unbound in oplasma being 0.36% and 0.50% in patients and healthy subjects, respectively. Apparent volume of distribution (Vd/F) of the terminal phase based on total plasma erdafitinib in healthy subjects is small (approximately 31 L), suggesting it is limited by the binding to plasma protein. Erdafitinib has low total plasma oral clearance (mean CL/F in subjects with cancer averaged 0.29 L/h; the corresponding value for healthy subjects was 0.43 L/h), likely restricted by protein binding. As a consequence, the apparent elimination half-life (t1/2) of erdafitinib is long (approximately 50 hours in healthy subjects) resulting an approximately 3- to 4-fold accumulation in Cmax and AUC following multiple daily dosing.

Erdafitinib is being investigated as an anti-cancer agent in several clinical studies (refer to most updated version of erdafitinib IB). As of June 2016, 305 subjects have been treated with erdafitinib. The median extent of drug exposure as of June 2016 was 7 weeks (range: 0 – 102 weeks). There does not appear to be any dose-related trends in mean or median drug exposure, suggestive of tolerability of the drug. As for clinical efficacy, responses were observed at doses of 9 mg once daily or higher (range of responses: ~12 – 40%), particularly in patients with FGFR mutations.

[figure not shown]

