**Notes:**

- Additional tests may be performed at the discretion of the treating investigator as clinically indicated. The sample collection schedules outlined above are based on an ideal subject.
- All appointment/procedures may be performed ± 3 days to accommodate unexpected scheduling issues, weekends and holidays.** The sample schedule should be followed as closely as is realistically possible; however, the schedule may be modified due to problems such as scheduling delays or conflicts (e.g., clinic closure, poor weather conditions, vacations, etc.).
- Shaded cells (gray) represent **RESEARCH** procedures; white cells represent **STANDARD OF CARE** procedures

- Pre-study assessments should be performed within 28 days prior to starting treatment, unless otherwise noted. Please note that the labs obtained on Cycle 1, Day 1 also need to meet eligibility criteria. Screening procedures (i.e. history and physical exam, etc.), excluding labs, which are conducted within 1 week of C1D1 do not need to be repeated. Labs performed on C1D1 for screening are permitted given that they are submitted to the Coordinating Center and approved prior to study treatment initiation.
- Chemistry includes measurement of sodium, potassium, chloride, bicarbonate, BUN, creatinine, glucose, total bilirubin, calcium, total protein, albumin, AST, ALT, and alkaline phosphatase.
- CT scans (chest/abdomen/pelvis) are acceptable for tumor evaluations. MRI of the brain is to be performed only at the discretion of treating physician. Baseline scans should be performed up to 4 weeks prior to study drugs initiation. The scans may be performed ± 5 days of patient's scheduled appointment, to accommodate weekends and holidays
- FFPE blocks may be from the primary tumor (time of original diagnosis) or a metastatic biopsy site. If available, a previously stored fresh-frozen tissue will also be collected. Tissue collected should be submitted at the time of registration. If patients are agreeable, at any time prior, during, or after study drug exposure, an optional (but encouraged) fresh-frozen tissue research biopsy of a metastatic site of disease will be performed and collected (see Section 10.3 for more details). It is assumed that about 20% patients will agree to a fresh biopsy.
- Pill Diary dispensed with study drug for all patients in the study.

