### **7.11 Replacement of Patients Who Discontinue Early**

In general, the study intends that patients would be treated until disease progression or intolerable toxicity. During the phase Ib dose escalation period and phase II portion of the study, if a patient discontinues study treatment for reasons clearly not related to study treatment, after completing fewer than one planned cycle of study, and/or receiving <75% of the total intended dose of study drugs over the first cycle of treatment, then that patient will be considered not evaluable and may be replaced with a new patient.

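### The RP2D rule keeps a fixed count of 15 tolerant patients, but the plan does not define who is in the denominator when a patient stops before week 8 for progression without toxicity

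*Combined protocol and SAP*

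**What the plan says.** Section 17.2.1, under the heading that justifies the RP2D, counts patients at the MTD who "can tolerate treatment for a minimum of 8 weeks in a row without development of the previously cited toxicities". It then restates the condition as "at least 15 out 20 patients are able to safely tolerate the combination at a given dose level" for 8 consecutive weeks. The table there gives the chance of seeing 15 or more tolerant patients out of 20 for a range of true tolerability values. The same text has drug given only until progression or unacceptable toxicity.

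Four other statements bear on who is counted:

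- The opening of 17.2.1 fixes the analysis set: "all patients who received at least 8 weeks of erdafitinib will be included in the" tolerability portion.
- Later in 17.2.1, 20 is a minimum for the expansion, and escalation patients treated at the MTD are added to the tolerability analysis.
- Section 17.3 says: "All patients included in the study must be assessed for safety, tolerability, and response to treatment, even if there are major protocol treatment deviations".
- Section 7.11 lets a patient be replaced who stops for reasons clearly unrelated to treatment "after completing fewer than one planned cycle of study" and/or with under 75% of the intended cycle 1 dose.

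Section 12 places the first response assessment after two cycles, and the study calendar notes add: "The scans may be performed ± 5 days of patient's scheduled appointment".

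**The concern.** Tolerance as written has two parts: staying on treatment for 8 weeks, and having none of the cited toxicities. Drug stops at progression, so a patient who progresses at week 6 with no toxicity fails the first part for a reason unrelated to tolerability. The opening of 17.2.1 takes that patient out of the set but leaves the required count at 15. Section 7.11 does not cover a stop in weeks 5 to 8 after adequate cycle 1 dosing.

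Scan timing matters too. Suppose a toxicity-free patient has progression on the first scan. If the scan is on Day 53 and drug stops that day, the patient has under 56 days of treatment. The same patient scanned on Day 58 has completed 8 weeks. Both days fall inside the permitted window.

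The analysis-set sentence also has an opposite effect. A patient who stops for toxicity before week 8 leaves the set as well, which would overstate tolerability.

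This rule selects the dose for phase II, and its printed pass probabilities hold only if exactly 20 patients are scored, each on tolerability alone.

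**Working it through.** **Inputs from the plan.** Threshold 15, denominator 20 and the table of pass probabilities (17.2.1). PFS medians of 9.2 months, and "3.8 months for fulvestrant plus placebo arm", from the phase III trial of fulvestrant with or without palbociclib (3.2.1).

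**Assumptions.** The plan gives no rate of progression before week 8. I write q for the probability of stopping before week 8 for progression without toxicity, and t for true tolerability, and take the two as independent. A month is 30.44 days.

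**Step 1: reproduce the table.** P(Bin(20, t) ≥ 15) at t = 0.3, 0.5, 0.7, 0.75, 0.8, 0.9 and 0.99 is 0.00004, 0.021, 0.416, 0.617, 0.804, 0.989 and 1.000. All agree with the printed values.

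**Step 2: 20 treated, early progressors removed, count still 15.** At t = 0.80:

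- two removed: P(Bin(18, 0.80) ≥ 15) = 0.50
- three removed: P(Bin(17, 0.80) ≥ 15) = 0.31

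**Step 3: 20 treated, early progression at rate q, no replacement.** Pass probability = P(Bin(20, t(1−q)) ≥ 15). With q = 5% and t = 0.80, the success probability is 0.80 × 0.95 = 0.76 and the pass probability is 0.66.

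**Step 4: q from the cited medians, cycle 1 stops replaced.** Only Days 29 to 56 then count. Under exponential PFS, q = 1 − exp(−ln 2 × (28/30.44)/median).

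| Median PFS | q, weeks 5–8 | 0.80 × (1−q) | Pass probability, N = 20 |
|---|---|---|---|
| 9.2 months | 6.7% | 0.746 | 0.60 |
| 3.8 months | 15.4% | 0.676 | 0.33 |

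These treat every progression in weeks 5 to 8 as a stop before Day 56.

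**Step 5: pooling escalation patients, count held at 15, no early progression.** N = 23 and 26 are illustrative.

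| True tolerability | N = 20 | N = 23 | N = 26 |
|---|---|---|---|
| 0.60 | 0.13 | 0.39 | 0.67 |
| 0.80 | 0.80 | 0.97 | 1.00 |

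A larger N offsets losses to progression, but it also passes a dose with tolerability 0.60 about five times as often (0.67/0.13).

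**Step 6: a proportion of evaluable patients instead.** With 20 treated, toxicity-free early progressors excluded, and at least 75% of the remainder required to be tolerant, the pass probability at t = 0.80 is 0.73 at q = 10% and 0.73 at q = 20%. The fixed count gives 0.50 and 0.22. With no intolerance (t = 1.0), the proportion rule always passes.

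**The case against.** A reader might infer that progression alone will make a well-tolerated dose fail. The documents do not establish that. It needs exactly 20 scored patients with at least six early progressors held against the count of 15, and nowhere does the plan score such patients as intolerant. If the 20 are read as 20 patients with at least 8 weeks of erdafitinib, progression cannot fail the dose and the printed table applies. What remains is that no section calls for enrolment to continue until there are 20 such patients. It would take 20/0.933, or 22 treated, at q = 6.7%, and 20/0.846, or 24, at q = 15.4%. The plan speaks of treating at least 20.

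Pooling also softens the loss. At the 3.8-month median with no intolerance, and with all progression to Day 56 counted (q = 28.5%), the pass probability is 0.47 at N = 20 but 0.82 at N = 23. That stands, at the price shown in Step 5.

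Counting all progression from Day 0 to Day 56 (13% and 28.5% at the two medians) would give 0.40 and 0.08 at t = 0.80. Those figures are too strong, because 7.11 allows cycle 1 stops to be replaced. Even the weeks 5 to 8 figures overstate the loss at the cited medians. With the first scan at about week 8, most radiographic progression would be found close to completion, and earlier stops would come mainly from clinical progression or early-window scans. The 3.8-month median belongs to a regimen without palbociclib, which nobody here is assigned. In the other direction, that trial enrolled patients naive to CDK4/6 inhibitors, while 4.2.2 accepts prior exposure. The true rate is unknown.

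Nor does the background statement that "The median extent of drug exposure as of June 2016 was 7 weeks" estimate early progression. It pools several studies, gives no reasons for stopping and may include patients still on drug.

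**Conclusion.** The point holds as an undefined and inconsistent denominator in the rule that selects the phase II dose. A toxicity-free patient who stops before week 8 for progression cannot be counted as tolerant, and the statements in 17.2.1, 17.3 and 7.11 do not agree on whether that patient is excluded, replaced or retained.

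If 20 are treated without replacement, the printed 0.80 at true tolerability 0.80 becomes 0.66 at an assumed 5% early progression. It becomes about 0.60 or 0.33 under exponential PFS at the two cited medians with cycle 1 stops replaced. The last two mark the upper end of the loss at those medians. All three rest on independence of progression and tolerability, and on rates the plan does not give. Pooling can reverse the loss, but with the count held at 15 it does so by lowering the bar.

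**What to change.** In 17.2.1, define the tolerability-evaluable set as patients treated at the dose who either complete 8 weeks, or have a cited toxicity or stop for toxicity before then. Exclude from the denominator, and report separately, patients who stop before week 8 for progression or another non-toxicity reason without a cited toxicity. State the criterion as at least 75% of evaluable patients tolerant, and restate the pass probabilities and Wilson intervals for the actual evaluable N. Align the analysis-set sentence, the sample-size and pooling text and the RP2D rule in 17.2.1 with 17.3.

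Add two sensitivity analyses: the number of 8-week completers among all treated, and the cumulative incidence of intolerance by Day 56 with non-toxicity stops as a competing event.

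The alternative of passing the dose if no more than 5 of 20 have an intolerance event is less suitable as the main rule. It treats the unobserved weeks of early progressors as passed, and so makes passing easier.

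The cost is wording and two extra summaries, with no added patients. The evaluable N may fall below 20, so precision drops slightly: the Wilson interval is 0.55 to 0.91 for 14 of 18, against 0.53 to 0.89 for 15 of 20. Rounding also moves the pass probability. At t = 0.80 it is 0.72 for 14 of 18 and 0.67 for 15 of 19, against 0.80 for 15 of 20, which is why the table should be restated by N.
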